Sample size calculation and power: From preliminary analyses it was evident that a minimum 8 vs 8 cluster/ arm trial would be required to adequately power the study to detect plausible effect sizes using a relatively simple cluster arm comparison for a single month's data (temporal variation is unknown so it is difficult to include multiple months in *a priori* power analysis). We used fixed assumptions for the number of available health centres/ zone of N=7 and number of ANC1 visitors

per month of N=20, giving a cluster size of N=140. Note that varying the cluster size has only a moderate impact on power, provided health centres are chosen randomly from those available. Parameter values for the inter-cluster coefficient of variation (*k*, which has a large impact on power) were estimated from DHIS2 2018 data from the rate of positive malaria tests per month per capita (i.e. data divided by population size of zone) as a proxy. Following equation 9 in Hayes & Bennett (1999) we calculated k=0.18 from these data. However, noting this is lower than estimated from the only comparable published study from Tanzania (k values of 0.20-0.28 depending on survey round; West et al. 2014) we also examined a 'high COV' value of k=0.3.

Similarly we lacked information on the baseline prevalence of malaria for Sud Ubangi, with the last survey in 2013-14 detecting a rate of 24% in children under 5 (MPSMRM 2013-14), which using a conversion factor of 1.44 between child and pregnant women's prevalences (van Eijk et al. 2015) we used to estimate an ANC prevalence value of 17%, which is also very close to the average figure for the DRC ANCs presented in Hellewell et al. (2018). However, figures in Hellewell vary greatly and thus because of the considerable uncertainty in this point estimate, we examined a range of possible prevalence rates (applicable to the standard-LLIN reference arm).

We identified the minimum detectable reduction in prevalence using equation 4 from Hayes & Bennett (1999) with the following study design parameters:

Arms=2; Clusters (zones)/arm = 8; subjects/ cluster = 140; k = 0.11 or 0.30; α =0.05; power =80%; prevalence in reference standard-LLIN arm (π 0) varied between 5 and 50%

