Results are shown in Figure 8, and suggest that the study design proposed will be capable of detecting a reduction in prevalence of less than the maximum obtained in the Tanzania Olyset + PBO LLIN trial (Protopopoff et al. 2018) even with the higher COV unless prevalence rates are much lower than expected and if the lower COV value is realistic the study has good prospect to detect the lower effect size seen in the Tanzania study with likely prevalence rates. Our data from Nord Ubangi suggest a greater entomological efficacy of Permanet 3 than Olyset + (Figure 3) but it is unclear whether this might translate into a larger epidemiological effect size than

Figure 8. Summary of power for ANC1 prevalence study based on sample size projections of 8 health zones/ arm, 7 health centres/ zone, 20 ANC1 visitors tested per month for two different values of the intercluster coefficient of variation. The plot shows the minimum % reduction in monthly prevalence in PBO vs non-PBO LLIN arms predicted to be detectable (with 80% power) as a function of *Plasmodium* prevalence in ANC1 visitors. Maximum and minimum % reduction estimates obtained in the Tanzania PBO (olyset +) vs standard (olyset) LLIN trial (Protopopoff et al. 2018) are superimposed for context.

obtained in the Tanzania Olyset+ trial. The split zone in Boto could provide one additional non-PBO cluster, if the distribution occurs as planned and can include sufficient health centres, but at present the sample size calculations and power analysis conservatively retain the 8 vs 8 design.

Procedures

ANC visitor recruitment

The recruitment process at each clinic will occur when women attend their first (second trimester) ANC appointment. Women will be asked if they would like to be enrolled in the study, the main

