Nurses at health centres would be responsible for this additional testing and treatment and for the enrolment of participants into the study. Training in administering RDTs and ACTs according to the protocol and filling the register and questionnaires will be organized by the DRC project coordinator

and facilitated by the Gemena-based epidemiological coordinator, in coordination with a representative of the PNLP. It is planned that the training will be conducted in five regional pools to optimize cost and logistical demands. One member of nursing staff per health centre included in the study will be formally trained, along with a representative from each health zone.

Secondary

(*i.e.* to be tested between PBO and non-PBO areas but study not specifically powered for these) RDT-confirmed monthly malaria cases and monthly severe malaria cases per capita. These data will be taken from DHIS2 which is updated monthly for all health centres in relation to population size estimates for each health zone. As noted earlier severe cases are quite rare with approximately 1/20 of the 83,150 malaria cases reported (and confirmed by RDT) in 2018 in the province being recorded as severe.

Epidemiology design summary: 8 zones per LLIN-type arm; 7 health centres per zone; 20 (or more) ANC1 women tested per health centre per month. *Provided the effect size is of the order seen in the Tanzania PBO trial, the design should be robust to variation in currently unknown parameters.*

Data analysis

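### The epidemiology design summary calls power robust to the unknown parameters, but the protocol's own power section makes it depend on k and on prevalence

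*Protocol*

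**What the plan says.** The closing statement on power is in the Protocol's epidemiology design summary. That summary lists 8 zones per arm, 7 health centres in each and at least 20 women tested monthly at every centre, and then concludes: "Provided the effect size is of the order seen in the Tanzania PBO trial, the design should be robust to variation in currently unknown parameters".

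The section on sample size calculation and power is more guarded:

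- It introduces k with a warning: "Parameter values for the inter-cluster coefficient of variation (*k*, which has a large impact on power".
- It gives k=0.18 from routine 2018 data, 0.20 to 0.28 from the one comparable published study, and 0.3 as a high value. The list of design parameters then reads "subjects/ cluster = 140; k = 0.11 or 0.30".
- Reference-arm prevalence is also unknown. The point estimate is 17% ("we used to estimate an ANC prevalence value of 17"), and because of its uncertainty the calculation "varied between 5 and 50" percent.
- The text around Figure 8 says that, at the higher k, a reduction smaller than the Tanzania maximum can be detected, provided prevalence is not far below what is expected.
- For the lower Tanzania effect it is more restrictive, in a sentence whose last words also limit the claim to plausible levels of prevalence: "if the lower COV value is realistic the study has good prospect to detect the lower effect size seen in the Tanzania study with likely".

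**The concern.** A design is robust to an unknown parameter if its power holds up over the plausible values of that parameter. The sample size section says the reverse for k, and it attaches a prevalence condition to both Tanzania effects. The summary keeps one condition only, that the effect be of Tanzania size. It does not say that only the larger Tanzania effect is meant.

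The summary is the sentence most likely to be quoted. The protocol plans quarterly analyses so that funders can assess the trial, and it expects donors to use the results when choosing nets. A reader who relies on the summary could give a non-significant month more weight against a moderate benefit than the design can bear.

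**Working it through.** **Inputs, all from the Protocol's sample size section**

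- Formula: "We identified the minimum detectable reduction in prevalence using equation 4 from Hayes & Bennett (1999").
- c = 8 zones per arm. n = 7 × 20 = 140 women per zone per month, which matches "giving a cluster size of N=140".
- Alpha 0.05 and power 80%. Sidedness is not stated, so two-sided is assumed: (1.960 + 0.842)² = 7.849.
- Prevalence p0 from 5% to 50%. The expected value is 24/1.44 = 16.7%, which matches the stated 17%.
- k = 0.11 and 0.30 (used), 0.18 (calculated), 0.28 (top of the published range).

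**Formula**

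c = 1 + 7.849 × [p0(1−p0)/n + p1(1−p1)/n + k²(p0² + p1²)] / (p0 − p1)², with p1 = p0 × (1 − reduction).

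The protocol's own results are in Figure 8, which is not shown in the text available, and no detectable reduction is given in words. Its curves therefore could not be reproduced.

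**Check at p0 = 17%, k = 0.30, reduction 44.2%**

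p1 = 0.0949. The bracket is 0.001008 + 0.000613 + 0.003411 = 0.005032, and (p0 − p1)² = 0.005646. So c = 1 + 7.849 × 0.005032/0.005646 = 8.0, as required.

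**Minimum reduction detectable with 80% power, one month**

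| k | p0=5% | 10% | 17% | 30% | 50% |
|---|---|---|---|---|---|
| 0.11 | 50% | 37% | 30% | 24% | 20% |
| 0.18 | 52% | 41% | 34% | 30% | 27% |
| 0.28 | 57% | 47% | 43% | 39% | 37% |
| 0.30 | 58% | 49% | 44% | 41% | 39% |

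A version with t quantiles on 14 degrees of freedom, without the added 1, agrees within about one percentage point of power.

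**Power for given reductions**

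Power = Φ(√[7(p0 − p1)²/bracket] − 1.960). For a 35% reduction from 17%, p1 = 0.1105 and (p0 − p1)² = 0.003540.

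- k = 0.30: bracket = 0.001008 + 0.000702 + 0.003700 = 0.005410. √(7 × 0.003540/0.005410) = 2.140, so power = Φ(0.180) = 57%.
- k = 0.18: the between-zone term falls to 0.001332 and the bracket to 0.003042. The root is 2.854, so power = Φ(0.894) = 81%.

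The lower Tanzania effect has no number in the text, so a range is shown, at 17% prevalence:

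| Reduction | k=0.18 | k=0.28 | k=0.30 |
|---|---|---|---|
| 30% | 67% | 47% | 44% |
| 35% | 81% | 61% | 57% |
| 40% | 91% | 74% | 70% |

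A 60% reduction has at least 83% power in every cell. The lowest is at k=0.30 and 5% prevalence.

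**The case against.** The strongest reply is that the protocol already states the conditions. The sample size section gives both, and the summary is hedged and carries no number. This is fair as far as it goes: no calculation in the protocol is shown to be wrong. But a summary that drops the conditions of the result it summarises states a different property, and the one it states does not follow.

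A second reply is that one month understates the trial. Main assessments are six-monthly, monthly data will be modelled over time, and 20 women per centre is a minimum. This has force at low prevalence. A 45% reduction at 5% prevalence has 55% to 70% power in one month for k from 0.30 down to 0.11. With six months pooled (n = 840, k unchanged, as an illustration), it has at least 86%. Pooling helps much less when k is high, because the between-zone term does not shrink. At k=0.30 and 17% prevalence, n = 840 gives 55% power for a 30% reduction and 70% for 35%. Even with unlimited women per zone the detectable reduction is 37.5%. The protocol itself bases its power on separate months.

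A reader might go further and infer that power for the lower Tanzania effect is far below 80%, or that the trial would miss that effect about as often as find it. The documents do not support this, because they never state that effect as a number. The sample size text suggests a bracket of roughly 30% to 44%: detectable at 17% prevalence with k=0.11, and not claimed with k=0.30. The floor rests on k=0.11 and would be 34% with the calculated 0.18. The ceiling treats silence about the high k as a statement that the effect cannot be detected. At k=0.30 and 17% prevalence, power runs from 44% to 80% across that bracket, so the severe reading fits only its lower end, or lower prevalence.

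Nor do the documents say that anyone will treat a non-significant result as evidence against benefit. That is a risk of the wording and not a stated plan.

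**Conclusion.** The point holds as an inconsistency within the protocol. The summary claims robustness to k and prevalence, while the sample size section makes detection depend on both, and the stated formula confirms the dependence. Across the protocol's own ranges the detectable reduction runs from about 20% to 58%. At 17% prevalence it rises from 30% to 44% between the two k values used.

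How far power falls for the lower Tanzania effect cannot be settled from the documents. For assumed effects of 30% to 40% at 17% prevalence it is 44% to 70% at k=0.30, and 67% to 91% at k=0.18. For an effect near 60% the summary's claim stands throughout.

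The figures assume two-sided alpha and one month's data. A one-sided test would lower every detectable reduction without removing the dependence on k and prevalence. The mismatch between the calculated k of 0.18 and the 0.11 in the parameter list is a separate matter. The point does not rest on it, since the gap already shows between 0.18 and 0.30.

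**What to change.** Replace the robustness sentence in the epidemiology design summary with a conditional one, for example:

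*For a single month's data the design has 80% power for reductions of about 34% (k=0.18) to 44% (k=0.30) at the expected 17% prevalence, and about 41% to 49% at 10% prevalence. Smaller reductions, which may include the lower Tanzania estimate, may be missed if k is high or prevalence is low. A non-significant result will be reported with its confidence interval and not read as excluding them.*

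If k is later re-estimated from trial data, estimate it within arms, for example under coded arm labels. An estimate over all 16 zones together absorbs the treatment effect. In a simulation with 140 women per zone, 17% reference prevalence and true k=0.18, a 44% reduction gave a median pooled k of about 0.34. Even with no effect, one month's estimate ranged from 0 to 0.28 (5th to 95th percentile).

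The cost is one or two sentences of wording and a less favourable power statement. Sample size, conduct and analysis are unchanged.

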Figure 2. Malaria case data January 2017-March 2019. Testing rates (by RDT) are generally very high and the majority of suspected cases are confirmed as malaria; severe malaria is uncommon.

Malaria entomology and Anopheles insecticide resistance: There are over 60 Anopheles species recorded in DRC of which approximately ten are thought to be malaria vectors. There is no published or unpublished information on the anopheline fauna of Sud Ubangi but our previous work - for a baseline survey preceding an AMF-funded LLIN distribution in April 2016 - from neighbouring Nord Ubangi province is likely to provide a useful indicator (Lynd et al. 2018). Collections from villages in two of the health zones in Nord Ubangi detected 84% Anopheles gambiae s.s., and all larval collections in pools in or near the villages were this species. Moreover, recent collections of adults during our scoping visit in April 2019 from Karawa, on the border of Nord and Sud Ubangi were composed solely of An. gambiae s.s (N=279). Resistance in Nord Ubangi was prevalent to deltamethrin and especially permethrin (Figure 3), likely in part a result of the ubiquity of target site mutations: all individuals possessed kdr 1014 mutations (>90% either 1014F/F or 1014F/S) and wild type (1014L/L) susceptible alleles were absent, a pattern also found in the recent collections in Karawa. However, importantly PBO had a strong effect on mortality in tube bioassays, almost fully returning susceptibility for deltamethrin. Preliminary testing of LLINs (N=2 for Permanet 2; N=1 for other LLINs) detected a very poor performance of Permanet 2, with zero mortality (and <1% knockdown), but much better performance of Permanet 3, especially from exposure to the top panel, which contains both PBO and deltamethrin. Overall these results suggested that, unless there are substantial effects on mosquito fitness not captured within the 24h mortality assessment period, first generation LLINs are likely to serve primarily as a physical barrier with limited wider community effect. Comparability of results for Nord and Sud Ubangi is yet to be determined but, give their proximity, the similarity of results from Karawa on the border of the provinces, and environmental similarity, there are no a priori reasons to expect major differences between the provinces in mosquito communities.

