implication of which for them is shown in the flow diagram below, i.e. they will be tested for malaria whether symptomatic or not. It will be made clear that there is no accepted benefit of either, and that the option is being offered solely for the purposes of our LLIN evaluation study. If, after asking any questions and discussing with friends or relatives as desired, they agree and sign the consent form, they will proceed via the lower route shown in the figure. If they do not wish to be included they will follow the route shown in the upper part of the diagram, which represents standard care. The decision will need to be taken within the timeframe of the appointment, and if a clear and certain decision is not reached by this time the standard care route will be followed.

Inclusion of health centres (aires de sante) in the study

The aires de sante (N=7) from each zone de sante (N=16) to be included in the study will be identified by random allocation from a list of functional aires de sante in a zone with >20 ANC1 visitors per month based on 2018 DHIS2 data.

Data collection and collation

Data collection should start at the first possible ANC before or just after (determined by RDT/ACT supply and training logistics) LLIN distribution. Recordings preceding the distribution would be beneficial but are unlikely to be feasible owing to time constraints.

It is proposed that study RDT results are recorded separately on the questionnaire form (appended) and transferred to the ANC register (observations section), rather than as a suspected or tested case in the standard register, which is the current procedure. The simple questionnaire will collect only essential information about the participant and their home environment as pertains to malaria risk and should be readily completed within the time waiting for the RDT result. Variables generated from the questionnaire data may serve as covariates in analyses although this is not planned *a priori*. ACT treatment would be administered to women testing positive in the RDTs. Data collected will be transferred monthly to Gemena in the same way as the DHIS2 data collation process, and passed to the study epidemiological coordinator.

Training

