All data will be analysed primarily on the basis of intention-to-treat. The primary outcome will be the prevalence of parasitaemia from the ANC visitor surveys, which will be compared between treatment arms using generalized linear Poisson mixed models with log link function to allow assessment of intra-cluster correlation, and correction factor to maintain type I error rate with a small number of clusters, but maintain power for the number of clusters in our study (Leyrat et al. 2017). Continuous (monthly) data will be available for each major endpoint analysis and will be analysed with time since LLIN distribution as a covariate. However, the power analysis above is based on separate monthly assessments. Interim endpoint analyses will be conducted quarterly, to allow ongoing assessment of the trial by funders. Meaningful baseline data will not be available for the study and therefore it is not intended to perform adjusted analyses *a priori*, though if systematic differences in influencing factors are identified, covariates may be incorporated into analyses. Blinding at the level of data collection is not possible because of the ready identifiability of the different types of LLINs. However, data source will be encoded prior to statistical endpoint analysis to ensure blinding.

Entomological

Primary

Hypothesis: PBO LLIN distribution will reduce the benefit of P450 metabolic-based enzymes and arrest selection on a key genomic area for resistance leading to lower frequencies in PBO-LLIN zones (via stasis or a fall) than observed in zones with standard LLINs (in which an increase is expected). In lay terms this is testing a hypothesis that PBO LLINs will reverse the increase in pyrethroid resistance; an effect which we should be able to capture using informative DNA markers for molecular surveillance.

Endpoint: comparative annual resistance marker frequency in *An. gambiae* measured using molecular surveillance diagnostics

Sample size calculation and power:

Entomological indices can be readily assessed at intervals with a periodicity of 6 months suggested as providing a good timeframe for a hypothesised change in marker frequencies. The work is

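### The reason given for planning no baseline adjustment does not hold for the secondary DHIS2 outcomes, and the open covariate clause should give way to named covariates

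*Protocol*

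**What the plan says.** The epidemiological *Data analysis* section covers all epidemiological outcomes, and its position on baseline is stated for the study as a whole: "Meaningful baseline data will not be available for the study and therefore it is not intended to perform adjusted analyses" a priori. The same sentence continues "though if systematic differences in influencing factors are identified, covariates may be incorporated into analyses". No covariate, criterion or time of decision is named. Under *Data collection and collation* the protocol adds "Variables generated from the questionnaire data may serve as covariates in analyses although this is not planned" a priori, and says of testing before the nets go out: "Recordings preceding the distribution would be beneficial but are unlikely to be feasible owing to time constraints".

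Other sections describe malaria data that predate distribution:

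- *Sample size calculation and power* (epidemiological): the values of k "were estimated from DHIS2 2018 data from the rate of positive malaria tests per month per capita", divided by zone population, as a proxy.
- Figure 2 is captioned "Malaria case data January 2017-March 2019".
- *Secondary* (epidemiological outcomes): confirmed and severe cases per capita. "These data will be taken from DHIS2 which is updated monthly for all health centres", in relation to each health zone's population.

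The *Data analysis* section also plans quarterly interim analyses, concedes that data collection cannot be blinded, and says that the data source will be coded before endpoint analysis.

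**The concern.** A single reason is given for having no planned adjustment, and it is applied to every epidemiological outcome. For confirmed and severe cases per capita, the pre-distribution DHIS2 rate is a baseline value of the outcome itself, from the same reporting system. Not using it gives up precision in a comparison of 8 against 8 zones.

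The replacement rule is also weak. Unnamed covariates may enter once differences have been noticed, in a trial analysed every quarter. This leaves the choice of model open after data are seen. The protocol itself states this rule, so it is not simply a detail left to a later analysis plan.

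**Working it through.** **1. Is a baseline available, outcome by outcome?**

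| Outcome | Source | Pre-distribution values |
|---|---|---|
| ANC1 prevalence (primary) | study RDTs | none expected; no routine testing in ANC |
| Confirmed cases per capita (secondary) | DHIS2, monthly | yes; 2018 zone rates of positive tests already used for k |
| Severe cases per capita (secondary) | DHIS2, monthly | same source; the 2018 province total is quoted |

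The stated reason is true of the first row and untrue of the other two.

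**2. How much could a baseline matter for confirmed cases?** The province had 83,150 cases in 2018, so 83,150/(16 × 12) ≈ 433 per zone-month. Poisson variance relative to the squared mean is 1/433 = 0.0023. The between-zone part, taking the protocol's k = 0.18 from this same measure, is 0.18² = 0.0324. The between-zone share is 0.0324/0.0347 ≈ 93%. Nearly all the noise is therefore of the kind that a zone baseline can address. The year-to-year correlation of zone rates is not given, so the gain itself cannot be computed.

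**3. Primary endpoint: inputs.** 8 zones per arm, 140 women per zone, two-sided α = 0.05 (sidedness assumed), power 80%. Reference prevalence is 17%, which reproduces: 24%/1.44 = 16.7%. The text gives k as 0.18 and 0.30; the printed parameter list has 0.11 in place of 0.18, a separate inconsistency treated here only as a range. Figure 8 is not shown, so no printed detectable reduction can be checked.

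**4. Unadjusted detectable reduction.** The formula is

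c = 1 + (1.96 + 0.84)² × [p0(1−p0)/m + p1(1−p1)/m + k²(p0² + p1²)]/(p0−p1)².

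With c = 8 and m = 140 it gives 29.8% (k = 0.11), 34.4% (k = 0.18) and 44.2% (k = 0.30). Check at k = 0.18: p1 = 0.17 × 0.656 = 0.1115. The within-zone term is (0.1411 + 0.0991)/140 = 0.00172 and the between-zone term is 0.0324 × (0.0289 + 0.0124) = 0.00134. Then 1 + 7.85 × 0.00306/0.0585² ≈ 8.0.

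The between-zone share of variance is 0.00134/0.00306 = 44%. Worked the same way, it is 23% at k = 0.11 and 68% at k = 0.30.

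**5. Effect of one zone-level covariate.** Let r be the correlation of the covariate with true zone ANC prevalence (assumed). The explained fraction is r² × share. Estimating the slope from 16 zones inflates the variance by about 1 + 1/(16−4) = 1.083. The variance multiplier is (1 − r² × share) × 1.083, and one of 14 degrees of freedom is lost.

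| r | Multiplier, k = 0.18 | Multiplier, k = 0.30 |
|---|---|---|
| 0.3 | 0.960 × 1.083 = 1.04 | 0.939 × 1.083 = 1.02 |
| 0.5 | 0.890 × 1.083 = 0.96 | 0.830 × 1.083 = 0.90 |
| 0.7 | 0.784 × 1.083 = 0.85 | 0.667 × 1.083 = 0.72 |

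Simulated zone-level analysis of covariance, at the unadjusted detectable effect, gives these powers (repeat runs agree to about one point; unadjusted about 80%, or 79.5% with 14 df):

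| r | k = 0.18 | k = 0.30 |
|---|---|---|
| 0.3 | 78% | 79% |
| 0.5 | 81% | 83% |
| 0.7 | 85% | 90% |

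At k = 0.11 the figures are about 77%, 78% and 80 to 81%. With r = 0, power falls to about 76%, a loss of 3 to 4 points.

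**The case against.** The strongest reply concerns the primary endpoint. The protocol says *meaningful* baseline data, which most naturally means ANC1 prevalence, and that is indeed absent. Using DHIS2 to approximate the spread between zones does not require zone rates to track ANC prevalence zone by zone. They may track it poorly: 83,150 cases among about 3.3 million people is 2.5% per capita per year, beside an assumed ANC prevalence of 17%. The protocol also reports an RDT stockout in October-November 2018 and is unsure whether rising counts reflect better data gathering. All of this stands, and it is why only a supportive adjusted analysis is proposed for that endpoint.

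A reader might infer a larger gain by shrinking k to k√(1−r²) and charging one degree of freedom. That gives 84% and 88% power at r = 0.5 and 0.7 (k = 0.18), or 86% and 92% (k = 0.30). It leaves out the cost of estimating a slope from 16 zones. With that cost included, adjustment loses power at r = 0.3 for every k examined.

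Coding the data source before analysis limits selective adjustment and deserves credit. It does not settle which covariates may enter, or when. An unseen analysis plan may list them, but the protocol's own sentence would still permit a choice after differences are seen.

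None of this answers the point for the secondary outcomes, where baseline and outcome are the same measure.

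**Conclusion.** The point holds in a limited form. For confirmed and severe cases per capita, the stated reason for no planned adjustment is untrue. Adjusting for the pre-distribution value is a standard and cheap way to gain precision there, although its size cannot be given without the correlation of zone rates over time. For ANC1 prevalence the statement is correct, and the value of a DHIS2 covariate runs from a loss of a few points of power to a gain of about 10, depending on r and k. These figures rest on assumed r, a single month, 17% prevalence and a normal approximation at zone level.

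Three stronger readings are not supported:

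- The unadjusted comparison is biased. It is not; allocation was randomised, and what is lost is precision.
- Between-zone variance dominates the primary analysis. This is so at k = 0.30, but the share is 44% at k = 0.18 and 23% at k = 0.11 for a single month.
- A full zone-level series for 2017-2019 is shown to be in hand. Zone rates are explicit for 2018 only; Figure 2's caption names no level, though DHIS2 is recorded by health centre.

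**What to change.** 1. For each secondary DHIS2 outcome, pre-specify as covariate the zone's pre-distribution rate of that same outcome over a fixed 12-month window. Choose the window with the October-November 2018 stockout in mind. With distribution projected for November 2019, the 12 months just before it (November 2018 to October 2019) would include a stockout month. October 2017 to September 2018 would not.
2. For ANC1 prevalence, keep the unadjusted model and add one pre-specified supportive analysis with a single covariate, the log pre-distribution confirmed-case rate of the zone.
3. Reword the baseline sentence so that it refers to ANC1 prevalence only.
4. Delete the clause that admits covariates after differences are identified, and bring the remark on questionnaire covariates into line with it.

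The cost is wording, plus retrieval of any DHIS2 months after March 2019 if a later window is chosen. In each adjusted model it is one degree of freedom and the slope estimate, about 3 to 4 points of power (at the effect size above) if the covariate is uninformative. For the primary endpoint that cost falls only on the supportive analysis.
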